355	anti-VEGF therapy that still meet eligibility criteria (see section 4.2) will be randomized.
356	"Persistent DME" at end of the run-in phase is defined as meeting all of the following:

257	CEE this langes (mission) on OCT meeting with an one of the fallowing true conden
357	CSF thickness (microns) on OCT meeting either one of the following two gender
358	and OCT machine-specific criteria:
359	• Zeiss Cirrus: ≥ 290 in women; ≥ 305 in men
360	• Heidelberg Spectralis: \geq 305 in women; \geq 320 in men
361 362	Visual acuity letter score ≤ 78 and ≥ 24 (approximate Snellen equivalent 20/32 to 20/320)
363	 DME is the cause of OCT thickening and vision loss by the investigator's
363 364	
365	judgment
	D. Tucotmont Cuoung
366 367	D. Treatment Groups
	Eligible study eyes at the end of the run-in phase will be assigned randomly (1:1) to one of the
368	following groups:
369 370	• Crown A. Shorn Lintrovitroal ramihizurrah
	Group A: Sham + intravitreal ranibizumab
371 372	Group B: Intravitreal dexamethasone +intravitreal ranibizumab
373	Study participants may have one or two study eyes. Study participants with two study eyes will
374	be randomized to receive continued anti-VEGF therapy (ranibizumab) in one eye and
375	
376	dexamethasone +ranibizumab in the other eye.
377	For both treatment groups, the initial ranibizumab injections must be given on the day of
378	
	randomization. The sham or dexamethasone injection will be given within 0-8 days of the
379	ranibizumab injection. Study eyes will be evaluated for retreatment every 4 weeks based on OCT
380	and visual acuity. Further details on the treatment schedule and criteria for retreatment are
381 382	included in section 4.8.
383	E. Sample Size
384	A minimum of 150 study eyes (from approximately 125 participants assuming 20% have two
385	
385	study eyes)
387	F. Duration of Follow-up
388	 Definition of Fonov up 12-week run-in phase prior to randomization
389	
390	• Primary outcome at 24 weeks after randomization
390 391	G. Follow-up Schedule
392	 Follow-up visits occur every 4±1 weeks
392 393	• Tonow-up visits occur every 4±1 weeks
393 394	H. Main Efficacy Outcomes
395	II. Main Encacy Oucomes
396	At 24 weeks after randomization:
397	
398	Primary:
399	Mean change in visual acuity letter score, adjusted for visual acuity at time of
400	randomization
401	
402	Secondary:

403		• Percent of eyes with at least 10 and at least 15 letter gain (increase) or loss
404		(decrease) in E-ETDRS letter score visual acuity

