759	Acuity-Refraction Testing Procedures Manual, and Study Procedures Manual).
760	Visual acuity testing, ocular exam, and OCT will be performed by DRCR.net
761	certified personnel.
762	• OCTs meeting DRCR.net criteria for manual grading may be sent to a reading center
763	but study participants' eligibility is determined by the site (i.e., individuals deemed
764	eligible by the investigator will be randomized without pre-randomization reading
765	center confirmation).
766	

767 768	1.	Electronic-ETDRS visual acuity testing at 3 meters using the Electronic Visual Acuity Tester (including protocol refraction) in each eye. (on day of randomization)
769		• This testing procedure has been validated against 4-meter ETDRS chart testing. ⁴⁵
770	2.	OCT on study eye (on day of randomization)
771 772	3.	Ocular examination on each eye including slit lamp, measurement of intraocular pressure, lens assessment, and dilated ophthalmoscopy (on day of randomization)
773	4.	Laboratory Testing- HbA1c
774 775 776		• HbA1c does not need to be repeated if available in the prior 3 months. If not available at the time of randomization, the individual may be enrolled but the test must be obtained within 3 weeks after randomization.
777 778 779	5.	Measurement of blood pressure
780	4.4	4 Randomization of Eligible Study Participants
781 782 783	1.	
784 785 786 787 788	2.	The baseline injections must be given on the day of randomization; therefore, a study participant should not be randomized until this is possible. For study participants with two study eyes, both eyes must be treated on the day of randomization. If the investigator is not willing to perform bilateral injections on the same day, only one eye should be randomized.
789 790 791		• Study participants with one study eye will be randomly assigned, with equal probability, to receive either:
792 793 794		 Group A: Sham + intravitreal ranibizumab 0.3 mg Group B: Intravitreal dexamethasone +intravitreal ranibizumab 0.3 mg
795		Randomization will be stratified by two factors:
796		1. Presence or absence of improvement in retinal thickness during the run-in phase,
797		defined as reduction in CSF thickness by 10% at any run-in visit, compared with the
798 799		prior visit.2. Presence or absence of improvement in visual acuity during the run-in phase, defined
800		as 5 or more letter gain in visual acuity at any run-in visit, compared with the prior
801		visit.
802		

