1147 The 0.7 mg dexamethasone implant (Ozurdex) generally appeared to be safe and well-tolerated in phase III studies in which it was evaluated as treatment for macular edema secondary to retinal 1148 1149 vein occlusion.⁴² No cases of endophthalmitis occurred in these studies which included 1,256 1150 study participants followed for 12 months after enrollment. The 12-month incidence of 1151 subconjunctival hemorrhage ranged from 22.3%-24.9% in study eyes, some of which received 1 1152 and some of which received 2 implants at either the 0.7 mg or 0.35 mg dose. Cataract 1153 progression occurred in 29.8% of phakic eyes that received two 0.7 mg implants versus only 1154 5.7% of sham-treated phakic eves. An increase in IOP of 10 mmHg or more was observed in 1155 eyes that received two 0.7 mg implants at rates of 12.6% after the first implant and 15.4% after the second treatment. A total of 32.8% of study eyes receiving two 0.7 mg implants had at least a 1156 1157 10 mmHg increase in IOP from baseline during the 12 months of follow-up. Of eyes that 1158 received a 0.7 mg implant at baseline, 25.5% were started on an IOP-lowering medication during the first 180 days of the study. When a single 0.7 mg dexamethasone implant was administered 1159 in 55 vitrectomized eyes with DME,⁴⁴ the most common adverse events were conjunctival 1160 1161 hemorrhage (52.7%), conjunctival hyperemia (20.0%), eye pain (16.4%), increased IOP (16.4%), conjunctival edema (12.7%), and vitreous hemorrhage (10.9%). Of the 48 study participants 1162 1163 who were not on IOP-lowering medication at baseline, 8 (17%) began on IOP-lowering medication during the study. Additional adverse events that occurred in more than 5% but less 1164 than 10% of eyes were maculopathy (either epiretinal membrane or macular thickening), anterior 1165 chamber cells, foreign body sensation, iritis, and floaters. Migration of Ozurdex to the anterior 1166 1167 chamber with subsequent corneal edema is a rare complication of Ozurdex injections. This risk is associated with with aphakic eyes, ⁵⁰⁻⁵² and pseudophakic eyes with anterior chamber intraocular 1168 lens and iridectomy or disruption of the posterior capsule.⁵³⁻⁵⁵ In one study of 342 eyes with 1169

- 1170 macular edema due to retinal vein occlusion treated with Ozurdex, two eyes (~0.5%) had
- 1171 Ozurdex dislocated to the anterior chamber requiring surgical repositioning in the vitreous

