1211 1212 1213 1214 1215	The approach to sample size and statistical analyses are summarized below. A detailed statistical analysis plan will be written and finalized prior to the completion of the study. The analysis plan synopsis in this chapter contains the framework of the anticipated final analysis plan.
1213 1216 1217 1218 1219 1220 1221 1222	This phase II clinical trial is conducted to assess the short term effect of combination steroid + anti-VEGF therapy on visual acuity and OCT retinal thickness, in comparison with that of continued anti-VEGF therapy alone, in eyes with persistent central-involved DME and visual acuity impairment despite previous anti-VEGF treatment. The primary outcome of the study will be the mean change in visual acuity at the 24-week post-randomization visit, adjusted for the baseline (randomization) visual acuity.
1222	The treatment groups include the following:
1224	• Group A: Sham + intravitreal ranibizumab 0.3 mg
1225	• Group B: Intravitreal dexamethasone +intravitreal ranibizumab 0.3 mg
1226	
1227	7.1 Sample Size
1228	This phase II study will include 75 study eyes (from approximately 62 participants) in each
1229	treatment group.
1230	
1231	The primary analysis consists of a statistical estimation of the difference in mean change in visual
1232	acuity letter score at the 24-week post-randomization visit, adjusted for the baseline visual acuity
1233 1234	and correlation between eyes, between the sham + ranibizumab group and the combination of corticosteroid+ ranibizumab group.
1234	concosteroid+ ramoizumao group.
1235	7.2 Sample Size Assumptions and Precision Estimates
1230	To estimate the standard deviation (SD) of change in visual acuity from baseline (randomization)
1238	to the 24-week visit (primary outcome visit), data from the DRCR.net Protocol I were reviewed.
1239	Of eyes that completed the 1-year visit, 61 eyes were identified at the 32-week visit to have 1)
1240	OCT CSF≥250 µm, 2) VA between 20/320 to 20/32; and 3) received at least 3 ranibizumab
1241	injections from the 16-week visit to prior to the 32 week-visit. All these eyes had received at least
1242	3 ranibizumab injections prior to the 16-week visit and met the OCT and VA thresholds above,
1243	mimicking the minimum number of injections required for enrollment into the run-in phase of this
1244	protocol. The mean change in visual acuity letter score from the 32-week visit (to mimic

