Diabetic Retinopathy Clinical Research Network

U1 Manuscript

Continued Ranibizumab With or Without Dexamethasone for Persistent Diabetic Macular Edema (Protocol U):

A DRCR.net Phase 2 Randomized Clinical Trial

Technical Plan

VERSION NUMBER	AUTHOR	APPROVER	EFFECTIVE DATE	REVISION DESCRIPTION
1.0	[name]	[name]	9-25-2017	Initial version

OVERVIEW

Protocol U is a short-term evaluation of combination intravitreous corticosteroid + anti-VEGF treatment for persistent central-involved diabetic macular edema following anti-VEGF therapy.

All potential study participants were required to participate in a 12-week run-in phase. In order to enter the run-in phase, all eligibility criteria were assessed and met. During the run-in phase, study eyes received 3 study ranibizumab 0.3mg injections approximately 4 weeks apart. At the end of the run-in phase, eligible study eyes that still met eligibility criteria were randomly assigned to one of the two treatment groups: A) sham + intravitreal ranibizumab 0.3mg [ranibizumab group], or B) dexamethasone intravitreal implant + intravitreous ranibizumab 0.3mg [combination group]. Study participants may have one or two study eyes. Study participants with two study eyes were randomly assigned to receive continued anti-VEGF therapy (ranibizumab) in one eye and dexamethasone intravitreal implant + ranibizumab in the other eye. Study duration was 24 weeks post randomization.

The protocol statistical analysis plan can be found at this location: \Eros\sys\user\aDRCRN\Protocols\Protocol U - Phase II Persistent DME Study\Statistics\SAP\Protocol U SAP 04-12-17 (8-29-17) ver 2 clean.docx

The purpose of this document is to provide the specific analysis objectives and technical details for the protocol U primary manuscript.

DATA SOURCE

Database used to create SAS data sets: DRCRnet_U_PrimManu_21sep2017

Data validation: \\Eros\sys\user\aDRCRN\Protocols\Protocol U - Phase II Persistent DME Study\Statistics\Data Closeout\Documentation

SAS master data sets

Dataset creation: \\Eros\sys\user\aDRCRN\Protocols\Protocol U - Phase II Persistent DME Study\Master Dataset\Documentation

Location: \\Eros\sys\user\aDRCRN\Protocols\Protocol U - Phase II Persistent DME Study\Master Dataset\Datasets\20170921Frz

SAS master datasets utilized:

- 1. *eyes* one record per eye (study eyes and non-study eyes)
 - a. Read in as *eyesRand*
 - i. Limited to randomized eyes only (randEyeFlg)

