- Report mean ± SD and median [IQR] by treatment group, adjusted mean difference, 95% CI and *P*-value from the treatment group comparison
- Sensitivity analysis [not in text]
 - All sensitivity analyses will mimic the primary analysis model using imputed data.
 - Pre-specified sensitivity analysis will be performed and stratified by sham injection procedure.
 - Post hoc sensitivity analysis will exclude all patients at Site 194.
 - Note: this was at recommendation of DSMC, after review of cases of ineligible participants enrolled at that site discovered at a site visit.
- Subgroup analysis (%*subgrpMixed* macro) [eTable 3]:
 - Pre-specified subgroup analysis will evaluate the effects of following baseline factors: lens status [eFigure 5], improvement in visual acuity during run-in phase [eFigure 6], and improvement in OCT during run-in phase [eFigure 7].
 - The subgroup analysis will mimic the primary analysis adding an interaction between subgroup and treatment to the primary mixed model using observed data only.
 - Report the *P*-value for the interaction term. Report mean ± SD and median [IQR] by treatment group within each subgroup.
 - Report adjusted treatment group mean difference and 95% confidence interval from treatment group comparison within each subgroup. Only in the presence of a significant interaction term (*P*<0.05) a within-subgroup *P*-value will be reported.
 - The effect of gender and race/ethnicity will be explored in the same way as the subgroup factors listed above. [not in text]
- iii. Secondary outcomes [Table 2]:
 - Binary outcomes: Perform binomial regression models with adjustment for same covariates in the primary analysis and use generalized estimating equations to account for correlation between eyes of bilateral participants. All outcomes will be

analyzed using imputed data except for the gender and OCT machine-specific outcome (%*MIAnalyzeBinary* macro).

- When binomial regression model failed to converge, a hierarchy is used to remove the covariates: laterality → improvement in OCT CST during run-in phase → randomization OCT CST.
 - This hierarchy was chosen based on judgment regarding theorized existence and strength of association with the outcome (least important → most important)
- Barnard's unconditional exact test will be used when binomial regression model failed to converge without any covariates (%MIAnalyzeBarnards macro).

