- Report the observed No. (%) by treatment group, adjusted difference in proportions, 95% confidence interval, and *P*value from treatment group comparisons
- AUC outcome: Mimic the linear mixed effect model in the primary analysis limiting the cohort to 24-week completers. No imputation will be performed.
 - Report mean ± SD and median [IQR] by treatment group, adjusted mean difference, 95% confidence interval, and *P*-value from treatment group comparison.
- 6. Summarize safety events occurred at any time during randomization phase
 - a. Ocular adverse events [eTable 5]
 - i. Tabulate No. (%) of eyes experienced at least one event by treatment group using *eyesRand* dataset
 - At least one ocular adverse events in the study eye
 - Increased intraocular pressure (IOP) events (a composite outcome, defined as any of the below). Each component will also be reported separately.
 - IOP increased \geq 10 mmHg from randomization at any visit
 - \circ IOP \geq 30 mmHg at any visit
 - Received ocular anti-hypertensives
 - Endophthalmitis
 - Inflammation
 - Any retinal detachment (a composite outcome, defined as any of the below). Each component will also be reported separately.
 - Traction retinal detachment
 - Rhegmatogenous retinal detachment
 - Unspecified retinal detachment
 - Retinal tears

- Retinal hemorrhage
- Vitreous hemorrhage
- Cataract extractions
- Glaucoma surgery
- Received post-injection treatment to lower IOP
- Migration of dexamethasone implant to the anterior chamber and subsequent corneal complications (combination group only)
 - Note: There is no specific MedDRA term for this type of adverse event. Instead, perform a manual check by searching for keywords "migration" and "anterior chamber" in the description field on the AE form, limiting to records in randomized eyes at post randomization.
- ii. Compare the frequency between treatment groups using Fisher's exact test and report *P*-value.
- iii. Footnote No. of patients experienced multiple types of ocular adverse events as listed above (if any)
- b. Systemic adverse events
 - i. All systemic adverse events will be reported by treatment group: combination group (unilateral participants), ranibizumab group (unilateral participants), and bilateral participants.
 - ii. Reduce *eyesRand* dataset to patient-level as a temporary dataset *ptRand*
 - iii. Tabulate No. (%) of participants experienced at least one event [eTable 6]
 - At least one systemic adverse event

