 - At least one serious systemic adverse event
 - At least one hospitalization
 - Death
 - APTC cardiovascular/cerebrovascular event (a composite outcome)
 - Non-fatal myocardial infarction
 - Non-fatal stroke
 - Death of vascular or unknown cause
 - iv. Compare frequency among unilateral participants between treatment groups using Fisher's exact test and report *P* value. [eTable 6]
 - v. Tabulate No. (%) of participants had at least one adverse event in each MedDRA system organ class [eTable 7]

References

 Tukey JW. The Future of Data Analysis. Ann. Math. Statist. 1962; 33(1):1-67. https://projecteuclid.org/euclid.aoms/1177704711#ui-tabs-1. Accessed 21 September 2017. 2. Schafer J. Multiple Imputation: A Primer. *Statistical Methods in Medical Research*. 1999(8):3-15.

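### Ocular adverse events are compared eye by eye with an unpaired Fisher test although each two-eye participant has one eye in each arm, so the P-values are too large when the two eyes are positively correlated

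*SAP*

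**What the plan says.** SAP item 6a(i) tabulates the number and percentage of eyes with at least one event in each arm, from the eye-level dataset. Item 6a(ii) then says "Compare the frequency between treatment groups using Fisher's exact test and report" the P-value. It mentions no pairing, stratification or clustering.

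The arms share participants. The SAP Overview says that those with "two study eyes were randomly assigned to receive continued anti-VEGF therapy (ranibizumab) in one eye and dexamethasone intravitreal implant" plus ranibizumab in the other eye. Protocol 1.3 D says the same: they will "be randomized to receive continued anti-VEGF therapy (ranibizumab) in one eye and" the combination in the other.

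Elsewhere the plan allows for this. Mean change in visual acuity and in central subfield thickness (CST) is modelled with a random subject effect (items 4b(ii), 5b(ii)). Binary efficacy outcomes use "generalized estimating equations to account for correlation between eyes of bilateral participants" (items 4b(iii), 5b(iii)). For systemic events, item 6b(iv) says "Compare frequency among unilateral participants between treatment groups using Fisher's exact test and report" the P-value, so two-eye participants are left out of that test.

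Protocol 7.5 leaves the method of safety analysis to the detailed SAP. Protocol 7.1 states: "This phase II study will include 75 study eyes (from approximately 62 participants) in each" treatment group.

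**The concern.** Fisher's exact test on a two-by-two table of eyes assumes that the two rows are independent samples. Here part of each row comes from the same people. With positive between-eye correlation, the difference between arms varies less than the test assumes, so P-values are on average too large. Type I error is not inflated; the cost is power to detect ocular harm.

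That matters because an intravitreal steroid is most likely to do harm in the treated eye, and assessing the safety of the combination is one of the study's stated aims (Protocol 1.2). Raised intraocular pressure (IOP) is the obvious example.

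There is a smaller parallel gap: the last-resort Barnard test for CST outcomes in item 5b(iii) also ignores the pairing.

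**Working it through.** **Structure of the sample.** Protocol 1.3 E and 2.1 plan 150 eyes with 20% of participants bilateral. 150 / 1.2 = 125 participants: 25 bilateral and 100 unilateral (50 per arm). Each arm has 50 + 25 = 75 eyes, from 75 different participants. One third of each arm is paired with the other. The 62 in Protocol 7.1 is 125 / 2 = 62.5, which would hold only if no participant contributed to both arms.

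**The plan's own figures.** No power or precision is stated for safety. For efficacy, Protocol 7.2 gives a 95% half-width of 2.3 letters (SD 7, 70 eyes per arm): 1.96 × 7 × √(2/70) = 2.32, reproduced. It adds that adjusting for between-eye correlation should slightly narrow the interval. With one third of eyes paired and an assumed correlation of 0.5, 1.96 × 7 × √[(2/70)(1 − 0.5/3)] = 2.12. The direction agrees; the same reasoning applies to event proportions.

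**Standard error, 10% v 25% (assumed rates).**
- Independent arms: v = 0.10 × 0.90/75 + 0.25 × 0.75/75 = 0.0037.
- Paired: v′ = v − 2 × 25 × cov/75². The documents give no correlation, so latent values of 0.3, 0.6 and 0.8 are assumed; these give cov = 0.0189, 0.0423, 0.0609 and v′ = 0.00353, 0.00332, 0.00316.
- Overstatement, √(v/v′) − 1: 2.3%, 5.5%, 8.2%.

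**Power at two-sided 0.05.** Simulation with 12,000 replicates per scenario, 25 pairs, and 50 unilateral eyes per arm in four strata (assumed sizes 13/13/12/12). The exact test combines stratum hypergeometric distributions with Binomial(discordant pairs, ½).

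| Latent correlation | Observed correlation at 10% v 25% | SE overstated | 10% v 25%: Fisher | exact | 10% v 20%: Fisher | exact |
|---|---|---|---|---|---|---|
| 0 | 0 | 0% | 61.1% | 61.2% | 32.0% | 31.9% |
| 0.3 | 0.15 | 2.3% | 61.5% | 63.7% | 31.5% | 33.0% |
| 0.6 | 0.33 | 5.5% | 62.0% | 66.4% | 30.6% | 34.5% |
| 0.8 | 0.47 | 8.2% | 61.1% | 67.9% | 30.9% | 37.1% |

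Larger effects gain less. Protocol 6.5.1.2 reports that, of eyes given the implant, "25.5% were started on an IOP-lowering medication during" the first 180 days. Against an assumed 5% control rate, at latent correlation 0.6, power is 94.6% (Fisher) v 95.4% (exact). For 15.4% (a 10 mmHg IOP rise after the second implant) against an assumed 2%, it is 81.8% v 83.4%.

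A separate simulation (60,000 runs, strata pooled, correlation set on the observed scale) agrees. At 10% v 25.5%, Fisher v paired exact is 63.7% v 63.7% at correlation 0, 64.3% v 68.4% at 0.3, and 65.1% v 71.8% at 0.5.

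**Type I error.** At common event rates of 10% and 20%, Fisher's falls from 2.7% and 3.0% (correlation 0) to 1.7% and 2.0% (latent 0.6); the exact test has 2.2% and 3.0% at 0.6. The shortfall from 5% at zero correlation is discreteness, which pairing does not remove.

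**Worked example.** Take 8 v 18 of 75 eyes: 5 v 12 among 50 unilateral eyes per arm and 3 v 6 among the 25 pairs. Fisher gives P = 0.051 whatever the pairing. With strata pooled, the paired exact P is 0.060, 0.049, 0.038 or 0.028 when 0, 1, 2 or 3 bilateral participants have events in both eyes.

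**The case against.** The strongest reply is that little depends on this. Counts per arm are reported for every ocular event and every IOP component, the Data and Safety Monitoring Committee reviews adverse events about every six months, and the trial is phase II. A large harm would be found either way. For cataract progression at 29.8% v 5.7% (Protocol 6.5.1.2), Fisher has at least 97% power. For a 10 mmHg rise at 32.8% against an assumed 10%, power is about 92–93% with Fisher and 93–94% with pairing. Rare events have low power under either test. The effect also shrinks with the bilateral share, which is itself a planning assumption: with 14 pairs (about 10%), the standard error is overstated by 1.3% and 3.0% at latent correlations 0.3 and 0.6, not 2.3% and 5.5%.

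Most of this stands, and it limits the size. It does not make an unpaired test fit a paired design. Cataract progression is also a weak counterexample, because the SAP lists cataract extraction. The loss falls on moderate differences, where a P-value is most likely to be consulted.

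Two further points are fair. The restriction in item 6b(iv) is better read as a matter of attribution, since a systemic event in someone receiving both regimens belongs to neither arm; it does not show that correlation was handled. And the worked example was placed near 0.05 to show the mechanism; it is not a forecast.

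**Conclusion.** The concern holds. As written, the ocular comparison ignores a dependence that the plan models for efficacy, and its P-values are conservative whenever the two eyes are positively correlated. The size is modest: at 10% v 25%, the standard error is overstated by 2.3 to 8.2% and 2.2 to 6.8 points of power are lost over latent correlations of 0.3 to 0.8, with under 2 points lost in the two larger-effect scenarios simulated at 0.6. At zero correlation nothing is lost.

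These figures rest on the planned 20% bilateral share, assumed correlations and assumed control rates. The protocol SAP cited in the SAP Overview was not among the documents, so a paired safety analysis there cannot be ruled out. The 62 participants in Protocol 7.1 is a wording error; power and precision are computed on eyes and do not change.

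**What to change.** In item 6a(ii), replace Fisher's test with an exact randomization test that swaps labels within bilateral pairs and permutes labels among unilateral eyes within the strata of Protocol 4.4 ("Randomization will be stratified by two factors"). Keep the number and percentage of eyes per arm, and report Fisher's test as a sensitivity result. The plan's GEE binomial model is an alternative where events are not sparse, but state the event-count threshold so that the choice does not follow the results.

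Label the change post hoc: the database name carries 21 September 2017 and the SAP took effect on 25 September 2017. Reconcile it with the cited protocol SAP if that sets another test. If the Barnard fallback is replaced too, state how results are combined over the 100 imputations.

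In Protocol 7.1, state 75 study eyes from 75 participants per group: about 50 unilateral, plus about 25 bilateral who give one eye to each group, with about 125 participants in all.

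The cost is a short program and one corrected sentence, with no new data. If the eyes are uncorrelated, the exact test gives up about 1 point of power at most (largest loss in the scenarios run: 47.0% v 45.7% at 5% v 15.4%).
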